Clinical study protocol

Project name: Comparison of traditional regression model and AI in predicting prolonged ICU stay after head and neck tumors

Sponsor: Sun Yat-sen Memorial Hospital of Sun Yat-sen University

Version number: V1.0

Version date: 2024.3.21

Project leader: [name]

Scheme signature confirmation: TBEV

-, Abstract of the study protocol

Title: Comparison of traditional regression model and AI to predict prolonged ICU stay after head and neck tumors

Brief description of the study: This experiment is a cohort observational study. By establishing a cohort of patients with head and neck tumors after surgery, we compared the prediction effect of AI and traditional prediction models on whether patients with ICU can be transferred to ICU within 24 hours after head and neck tumors after surgery. First, retrospective analysis of postoperative patients with head and neck tumors, patients' medical records were collected, and the patients were divided into training group and validation group according to 7:3, divided into 2 groups according to whether the ICU stay time was greater than 24 hours, and the prediction model of postoperative ICU stay time of head and neck tumors over 24 hours was established after using LASSO regression to select variables. At the same time, the data was cleaned, the AI was trained, and the efficacy was compared by ROC. After the establishment of prediction model and AI training, the patients included in the cohort were evaluated by prediction model and AI evaluation immediately after transfer to the ICU, which predicted the possibility of transferring out of the ICU within 24 hours.

Study jects: All patients with head and neck tumors

Outcome measures: The patient was transferred out of the ICU Sample size: Following the principle of 10 times the sample size, the included sample size is more than 10 times of the final variable, and 500 patients are currently expected to be included.

2. Research background (including the introduction of the disease, the treatment status at home and abroad, the significance of the research, etc.)

Head and neck tumor incidence ranks the sixth [1] in the global tumor incidence.

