3.1.2 Secondary Purpose

Explore the construction method and influencing factors of ICU stay time prediction model after head and neck cancer surgery.

4. research design

This study is a cohort observational study by establishing a retrospective cohort of patients transferred to ICU for head and neck tumors from January 2022 to December 2023, which is exempt from informed consent. Screen the variables to establish the traditional prediction model and train the AI, and then compare the accuracy of the traditional prediction model and the AI. After the validation on the basis of retrospective study of the traditional model and the prediction of AI for head and neck tumor patients postoperative ICU stay time, prospectively into the head and neck tumor postoperative ICU patients, the patient in the ICU to sign the waste specimen use consent, through prospective studies to verify the AI in ICU stay time prediction superiority.

5. Research protocol and technical route (including the calculation of study sample size, inclusion, exclusion, withdrawal criteria, evaluation indicators and methods of study results, statistical analysis plan, informed consent, ethics, etc.)

Sample size: Following the principle of 10 times the sample size, the included sample size is more than 10 times of the final variable. Currently, 500 retrospective patients and 200 prospective patients are expected to be included.

Selection criteria

Patients after head and neck tumors, older than 18 years.

Exclusion criteria

1 Patients transferred to ICU twice after head and neck tumors

2. Patients with unplanned transfer to the ICU

Evaluation indicators and methods of the results: compare the effectiveness of the model using accuracy or ROC

Statistical analysis plan: data description of statistical analysis, analysis methods of primary / secondary indicators / safety indicators, statistical school positive methods, control of bias, stratification / subgroup / sensitivity analysis, etc

All data were statistically analyzed using SPSS 25.0 and R languages, and P <0.05 was considered statistically significant.

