The measurement data conforming to the normal distribution are described by the mean standard deviation \pm (x \pm s); the measurement data that do not conform to the normal distribution are described by the median (M) and interquartile spacing (P25-P75); the counting data are described by frequency and percentage (%); the lacking measurement data are filled by mean, and the missing counting data is filled by mean.

Comparison of differences between groups: t-test was used for the measurement data meeting the normal distribution, rank sum test for the measurement data, \times 2 test, Fisher exact probability method or continuous corrected chi-square test for the counting data.

Informed consent: Exemption from informed consent for retrospective part. Signed informed consent for transfer to ICU.

VI. Safety evaluation (including the definition and assessment of adverse events and serious adverse events)

There is no direct interventional operation in this study, and the risks mainly include possible errors in data collection and management, as well as patient privacy protection issues.

Vii. Data collection and management

All data are retrieved and cleaned after export from the big data system. All data are retrieved by the database software. The relevant data are as

follows:

Baseline data:

Patients collected from the electronic medical records of admission baseline data: age, gender, Body Mass Index, body mass index (BMI), past history [including oral cancer treatment (radiotherapy, chemotherapy, immunotherapy), previous basic disease history (hypertension, diabetes history)], personal history (including smoking history, drinking history), family history of oral cancer, tumor site; Pre-operative indicators:

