(1) Clinical Assessment Scale: Nutritional Risk Screening Scale (Nutritional Risk Screening-2002, NRS-2002) (see Supplementary Table 1); (2) Preoperative laboratory examination results: blood routine [white blood cell count $(10^9/$ L), hemoglobin (g / L), platelets $(10^9/$ L), neutrophil count $(10^9/$ L), lymphocyte count $(10^9/$ L), monocyte cell count $(10^9/$ L), red blood cell volume (fL), the ratio of neutrophil count to lymphocyte count (Neutrophil-to-Lymphocyte Ratio, NLR), the ratio of lymphocyte count to monocyte count (Lymphocyte-to-Monocyte Ratio, LMR)], Coagulation function [plasma prothrombin time (s), fibrinogen (g / L), activated partial thromboplastin time (s), thrombin time (s), D-dimer (mg/L)], Liver function [glutamate aminotransferase (U / L), glutamate aminotransferase (U / L), albumin (g / L)), Renal function (creatinine (u mol/L)], Blood electrolytes [potassium ion (mmol/L), sodium ion (mmol/L), calcium ion (mmol/L), chloride ion (mmol/L)];

Procedure-related indicators:

Operation duration (h), flap type (none, fibula, femur, pectoralis major), scope of cervical lymph node dissection (none, unilateral, bilateral); Index of postoperative monitoring:

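### Filling missing categorical data with the mean is wrong as written (minor): for flap type and tumor site a mean is generally not a category

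*Protocol*

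**What the plan says.** The rule is in the protocol, section 5, statistical analysis plan: "the lacking measurement data are filled by mean, and the missing counting data is filled by mean". Both data types get the same statistic.

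The same plan shows what counting data means here. For description, "the counting data are described by frequency and percentage". For group comparison it names the "Fisher exact probability method or continuous corrected chi-square test for the counting data". These are methods for categorical variables. The blood cell counts in section VII carry units and are measurements, so the clause is not about them.

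Section VII lists the categorical items. The baseline list ends with "family history of oral cancer, tumor site", and the procedure-related list has "flap type (none, fibula, femur, pectoralis major), scope of cervical lymph node dissection (none, unilateral, bilateral". No other section gives a different fill rule, a coding scheme or an exception for categorical items.

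The abstract says that "the patients were divided into training group and validation group according to 7:3", with LASSO used to select variables. The secondary purpose (section 3.1.2) is to "Explore the construction method and influencing factors of ICU stay time prediction model".

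**The concern.** A mean needs a numerical scale. Flap type has four levels with no order, and tumor site is unordered by nature, although its levels are not listed. If such levels are stored as integers and averaged, the filled value usually falls between codes. Where it falls depends on how the levels happen to be numbered. Rounding returns a valid code, but which flap type that code stands for is again set by the numbering. Two analysts who both follow the sentence could give the same patient different flap types.

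For a two-level item coded 0/1 the mean is the prevalence. That is a usable number in a regression, but it is neither of the two levels, so it fits no row of a frequency table and no cell of a chi-square or Fisher test.

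At stake is how cleanly these items enter the LASSO and are read as influencing factors under the secondary purpose.

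**Working it through.** The protocol states no missing rate, category share or coding, so there is no figure of its own to reproduce. The check counts how many items are reached and then illustrates the coding problem.

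**1. Reach (section VII).** Listed candidates: baseline 12 + preoperative 23 + procedure 3 + postoperative 36 = 74. Categorical items:

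- unordered, several levels: flap type, tumor site (2)
- arguably ordered: scope of neck dissection (1)
- read as two-level: gender, radiotherapy, chemotherapy, immunotherapy, hypertension, diabetes, smoking, drinking, family history (9; the protocol does not list levels for smoking or drinking)

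Total 2 + 1 + 9 = 12 of 74. The training set is 0.7 × 500 = 350 of the retrospective patients. If an item were 5% or 10% missing (assumed), 25 or 50 of 500 patients would receive the fill, about 18 or 35 of them in training.

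**2. Flap type under integer codes.** Assumed shares: none 30%, fibula 20%, femur 40%, pectoralis major 10%. Fill = sum of share × code. Four of the 24 ways to assign codes 0 to 3:

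| Order of codes 0, 1, 2, 3 | Fill | Nearest code means |
|---|---|---|
| none, fibula, femur, pectoralis | 0 + 0.2 + 0.8 + 0.3 = 1.3 | fibula |
| femur, none, fibula, pectoralis | 0 + 0.3 + 0.4 + 0.3 = 1.0 | none |
| none, femur, fibula, pectoralis | 0 + 0.4 + 0.4 + 0.3 = 1.1 | femur |
| femur, pectoralis, none, fibula | 0 + 0.1 + 0.6 + 0.6 = 1.3 | pectoralis |

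Over all 24 codings the fill runs from 1.0 to 2.0 and is a whole number in 2. Rounded, it gives none 6 times, fibula 6, femur (the most common type) 7 and pectoralis 5. With assumed shares of 25/15/50/10% or 10/20/60/10%, the rounded fill is the most common type in 10 or 12 of 24 codings. A mode fill gives it in 24 of 24.

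**3. Dissection scope.** Coded 0/1/2 with assumed shares 30/50/20%, the mean is 0.5 + 0.4 = 0.9. This is a usable score but not one of the three levels.

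**4. Two-level items, only if the group tests use filled data and keep the filled value as its own level.** The prevalence becomes a third level, and a test with 1 degree of freedom (critical value 3.84) becomes one with 2 (5.99). Take an item with 80% power on complete data (noncentrality 7.849) and missingness m unrelated to the outcome group. The noncentrality becomes 7.849 × (1 − m):

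- m = 5%: 7.457; power 78.0% on observed values, 68.5% on filled values
- m = 10%: 7.064; power 75.7% on observed values, 66.0% on filled values

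The protocol does not say whether tests use filled or observed values, so this is a conditional illustration only.

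**The case against.** **It may be a slip.** Two clauses that name the same statistic would be redundant, and nearby sentences show translation errors (the chi-square test appears as a times-2 test). If mode was meant, the main point is settled by changing one word. The document does not say so, and the text as it stands is what an analyst would follow. The slip explains the error but does not remove it.

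**Coding dependence is not inevitable.** If unordered items are expanded into indicator columns, the mean is a set of proportions that does not depend on numbering and that a regression can use. The coding is not stated, so this may be what happens. The proportions would still have no place in frequency tables or exact tests. Nor is the mean of integer codes never a category: it is a whole number in 2 of the 24 codings above.

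**Most items are mildly affected.** For the nine two-level items and dissection scope, a regression can use the filled value. This stands, and it confines the serious case to two items.

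**Processing steps are kept.** The quality management plan retains each data processing step. That makes the fill traceable afterwards. It does not fix the coding in advance or make the rule suit categories.

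**Stronger readings that the document does not support.** A reader might infer that the rule biases the comparison of AI with regression, or that the group tests lose about ten points of power. The first is not shown anywhere. The second needs assumed gaps and tests run on filled data. A reader might also fault mean filling of skewed measurements because "the measurement data that do not conform to the normal distribution are described by the median (M"). Describing by the median does not oblige filling by it. That choice, and whether the two cell-count ratios (NLR, LMR) are recomputed after filling, is preference or detail and not part of this error.

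**Conclusion.** The clause on counting data is wrong as written, and the point is minor. That the rule conflicts with the plan's own treatment of counting data as categories follows from the text and needs no assumption.

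The size of any effect cannot be established. It depends on missing rates and coding that the protocol does not give. The numbering problem concerns 2 of 74 candidates, arises only if they have gaps, and needs integer codes. The shares, missing fractions and power figures above are illustrations under stated assumptions. No effect on the main purpose in section 3.1.1 is shown. The case for acting is that the sentence cannot be applied sensibly to categories and is almost free to correct.

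**What to change.** Replace the counting-data clause with: *Missing categorical values are assigned the training-set mode (or a separate 'missing' category; state which). The same fill is applied to the validation and prospective patients and to both models. Frequency tables and group tests use observed values.* The last sentence is needed because a missing category would itself add a level to the tests. If mode was meant, correcting that word settles the main point.

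The cost is a few sentences and a few lines of code in R or SPSS, both already named, with no new data. There are two downsides to weigh:

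- **Mode fill** pulls an item slightly toward its common level. A two-level item at 30% becomes 0.30 × 0.95 = 28.5% at 5% missing and 0.30 × 0.90 = 27% at 10%.
- **A missing category** avoids that but adds up to 12 columns to a LASSO fitted on about 350 training patients.

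Either way it remains a single fill that understates uncertainty. Multiple imputation, median fill for skewed measurements and recomputing the two ratios are optional.

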The incidence of head and neck tumors is increasing in China and is expected to reach 3.99 [2] per 100,000 people by 2049. Surgical resection has been identified as the primary treatment for oral cancer [3]. Because of the complex anatomy of the oral region, limited surgical space, and the need for simultaneous flap reconstruction to protect the integrity of the oral and maxillofacial systems, about 80% of patients undergoing oral cancer surgery will be transferred to the intensive care unit (ICU) after the operation, [4].

Previous studies found that prolonged ICU stay was associated with poorer prognosis and quality of life, causing a substantial disease and economic burden of [4]. ICU stay> 24 h implies a higher risk of nosocomial infection [5-7] and worsen the prognosis [8] in oral cancer patients. Previous studies found that ICU admission delayed oral feeding time and negatively correlated with 5-year survival [8,9]. Therefore, it is important to identify oral cancer patients with a long ICU after surgery.

Most patients with head and neck tumors have postoperative ICU stay time between 24 and 72 hours [10-12]. In a retrospective study of the UK National Intensive Care database, the median stay of patients undergoing head and neck cancer surgery was found in the ICU of 24 hours (IQR 18.8-46 hours) [13]. Meanwhile, according to our clinical experience, we believe that the ICU stay time of postoperative head and neck tumor patients should be within 24 hours is reasonable.

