(1) Clinical assessment scale: Acute Physiological and Chronic Health Assessment II score (Acute Physiology and Chronic Health Evaluation II, APACHE II), Sequential Organ failure score (Sequential Organ Failure Assessment, SOFA), Caprini venous thrombosis risk score; (2) Related indicators of ICU monitoring: time of mechanical ventilation, body temperature [mean body temperature in the first 24h after transfer to ICU (°C), highest body temperature (°C) in the first 24h after transfer to ICU, minimum body temperature $(^{\circ}C)$], arterial pressure [mean arterial pressure (mmHg) in the first 24h after transfer to ICU, highest mean arterial pressure (mmHg) in the first 24h after transfer to ICU, lowest mean arterial pressure (mmHg) in the first 24h after transfer to ICU]; ③ First postoperative laboratory examination: blood routine [white blood cell count $(10^{9}/$ L), hemoglobin (g / L), platelets $(10^{9}/$ L), neutrophil count $(10^{\circ}/L)$, lymphocyte count $(10^{\circ}/L)$, monocyte cell count $(10^{9}/$ L), red blood cell volume (fL), NLR, LMR], Coagulation function [plasma prothrombin time (s), fibrinogen (g / L), activated partial thromboplastin time (s), thrombin time (s), D-dimer (mg/L)], Liver aminotransferase (U / L), function [glutamate glutamate transaminotransferase (U / L), albumin (g / L)], Renal function [creatinine (u mol/L)), Blood electrolytes (potassium ion (mmol/L), sodium ion (mmol/L), calcium ion (mmol/L), chloride ion (mmol/L)]; Blood gas analysis [pH, partial pressure of carbon dioxide (kPa), partial pressure of oxygen (kPa), lactic acid (mmol/L)].

八、 Quality management plan (please introduce relevant measures to ensure project quality and progress)

Data processing by special person, in addition, data review by special personnel to determine the authenticity of the data, each data processing steps are retained to ensure the repeatability of the experiment.

IX. Pre-assessment and risk control plan of project risk benefits (Please describe the risks and benefits of the researchers, subjects and the medical institution; if there are risks, please introduce the measures and feasibility of risk control.)

By comparing the ICU stay time of head and neck cancer, it is expected

to improve the efficiency of postoperative management of head and neck cancer patients and reduce the waste of medical resources.

X. References

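### The models are to be scored on ICU arrival, yet the only variable list includes summaries over the first 24 hours in ICU and nothing bars them as predictors

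*Protocol*

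**What the plan says.** **When the models are applied.** The Abstract says that, once the models are built, "the patients included in the cohort were evaluated by prediction model and AI evaluation immediately after transfer to the ICU". The target is transfer out within 24 hours.

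**Outcome.** Patients are "divided into 2 groups according to whether the ICU stay time was greater than 24 hours".

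**How predictors are chosen.** The Abstract says the regression model "was established after using LASSO regression to select variables". Section 4 (research design) says only: "Screen the variables to establish the traditional prediction model and train the AI". Section 2 says that both models draw on the patient's clinical data. None of these limits the candidates by the time at which a value becomes available.

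**What is collected.** Section VII holds the only list of variables. Its ICU-monitoring item includes "time of mechanical ventilation, body temperature [mean body temperature in the first 24h after transfer to ICU" and, further on, "highest mean arterial pressure (mmHg) in the first 24h after transfer to ICU". No variable on the list is marked as descriptive only.

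**The concern.** A prediction made on arrival can use only what is known on arrival. A summary over the first 24 hours is complete at hour 24, which is when the outcome is decided. Two problems follow if such variables enter the models.

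- **The models cannot be used as described.** A model that needs the highest arterial pressure over 24 hours cannot be run at hour 0 in the 200 prospective patients.
- **Measured performance can be inflated.** A patient who leaves at hour 15 contributes 15 hours of readings, and one who stays contributes 24. More readings push the maximum up and the minimum down, so these summaries partly encode length of stay even when physiology has nothing to do with it.

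Ventilation time may be worse. If it is counted over the ICU stay, a value above 24 hours by itself implies a stay above 24 hours.

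The main purpose (section 3.1.1) is prediction accuracy, judged by accuracy or ROC, so this touches the study's principal result.

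**Working it through.** The protocol states no figure to reproduce. The check is a comparison of timing, followed by an illustration of size.

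**1. Timing of the seven ICU-monitoring variables (Section VII)**

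| Variable | Stated window | Complete at arrival? |
|---|---|---|
| Mean temperature | first 24 h | No |
| Highest temperature | first 24 h | No |
| Minimum temperature | none stated | Unclear |
| Mean of mean arterial pressure (MAP) | first 24 h | No |
| Highest MAP | first 24 h | No |
| Lowest MAP | first 24 h | No |
| Time of mechanical ventilation | none stated | Not if it is a duration in ICU |

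Five are explicit 0-24 h summaries and two have no window. The whole of Section VII has about 74 items by my count, so removing all seven leaves at most 74 - 7 = 67. The list contains no arrival temperature or arrival MAP that could replace the summaries.

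**2. How often the window would be cut short**

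Section 2 cites UK data with a median stay of 24 h and quartiles of 18.8 and 46 h. If these applied here (an assumption), about half of patients would have left by the time the window closes. A quarter would contribute at most 18.8 h, so at least (24 - 18.8)/24 = 22% of their window would be missing.

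**3. Why truncation alone creates a signal**

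Take independent readings with the same distribution in every patient. The chance that the largest of *m* readings exceeds the largest of *n* is *m*/(*m* + *n*). With hourly readings, 24 against 18 gives 24/42 = 0.57, and 24 against 10 gives 24/34 = 0.71. Both would be 0.50 without truncation.

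**4. Simulation under no true association**

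- Inputs from the protocol: stay quartiles 18.8/24/46 h; outcome stay > 24 h.
- Assumed: shortest stay 10 h and longest 120 h; hourly readings; two independent autocorrelated signals (temperature, MAP) unrelated to stay, with hourly correlation 0, 0.5 or 0.9 and between-patient SD 0 or 1; window = min(stay, 24 h).
- 40,000 patients per scenario, half held out.

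| Predictor | AUC for stay > 24 h |
|---|---|
| 24 h maximum | 0.53-0.58 |
| 24 h minimum (lower value scored as higher risk) | 0.53-0.57 |
| 24 h mean | about 0.50 |
| Five listed summaries, logistic, held out | 0.62-0.67 |
| First temperature and MAP readings | 0.49-0.51 |

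With the shortest stay at 4, 10 or 14 h and readings every 1 or 4 h (36 scenarios), the maximum gave 0.52-0.62 and the five summaries 0.58-0.73. Gradient boosting minus logistic regression ranged from -0.011 to +0.023, so neither type of model gained consistently.

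**5. Ventilation time**

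Taken as a random fraction of the ICU stay (an assumption), it gave an AUC of about 0.80-0.83. That is much larger, but it depends wholly on how the variable is defined.

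**The case against.** Section VII is a list of data to collect. It is not declared to be the predictor set, and an analysis plan that is not shown could restrict the candidates, so the harm is conditional on these variables being entered and retained. The scoring time appears once, in the Abstract, and describes the stage after model building, so the direct contradiction is with the prospective part. The comparison of AI with regression is not shown to be biased. The 24 h means do not leak by truncation on their own. Minimum temperature probably shares its neighbours' window, with the words lost in translation.

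The size is also uncertain. Section 2 says, just before the UK figures, that most patients stay between 24 and 72 h, which would mean fewer truncated windows. If only 20% leave early, all between 18 and 24 h (an assumption), the maximum falls to about 0.52 and the five summaries to 0.57-0.60.

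Most of this stands as a limit on the claim. It does not remove the conflict. The protocol itself fixes the scoring time, and its only list contains values that cannot exist then. The plan screens variables without qualification. Removing the summaries at the analysis stage would leave no arrival vital signs if the data pull follows the list. The prospective stage would expose the problem only after the models are built, and not at all if those patients are scored later from completed records.

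**Conclusion.** The concern holds as an unreconciled conflict between the stated prediction time and the listed variables. It must be fixed before the models are built. Five variables cannot be known at scoring, and two more are undefined in time.

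That conclusion needs no simulation. The AUC figures show the direction of the bias and that it need not be trivial; they are not an estimate for this hospital. They rest on the UK stay quartiles and on assumed stay limits, reading frequency and autocorrelation. Inflation would arise only if the variables are retained. There is no basis for saying that it would favour the AI over regression.

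**What to change.** State the prediction time in the protocol and apply one eligibility rule to both models and both cohorts. Either of two routes works.

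- **Option A: predict on arrival, as the Abstract says.** Admit only values known at that moment. Drop the first-24-hour summaries and ventilation duration as predictors, or replace them with the first recorded temperature and MAP and with ventilation status on arrival (yes/no). Use APACHE II, SOFA and the first postoperative laboratory and blood gas results only if they rest on data available at that time, and state their time window.
- **Option B: predict later.** State the time, restrict the analysis to patients still in the ICU then, and use only data up to that time.

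Under either option, the 0-24 h variables may still be collected for description if they are marked as not eligible as predictors.

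The cost is protocol wording and a revised pull from the same electronic records. The reported AUC will probably be lower. Option B also loses the patients who have already left the ICU.
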